8. STUDY INTERVENTION

8.1 Identity of Investigational Products (treatment / medical device)

8.1.1 Experimental Intervention (treatment / medical device)

Name: MagPro R30 with theta burst option

Manufacturer: MagVenture, Inc. Atlanta GA, USA

The device is CE certified according to ISO-Norm 13485:2003 and approved for clinical use.

Active stimulation: 1 Hz stimulation of 17 mins over left SMA, 15 sessions in total (5 per week)

8.1.2 Control Intervention (standard/routine/comparator treatment / medical device)

All stimulations are delivered with the same device. The stimulation sites are the same (left SMA) for all groups. The iTBS protocol is shorter (3 mins), the placebo protocol will be delivered with a specific placebo-coil that looks identical, makes identical sounds but produces no magnetic pulses.

Placebo control: 1 Hz stimulation of 17 mins over left SMA without magnetic emission, 15 sessions in total (5 per week)

Active control: iTBS stimulation over left SMA, 21 mins per session, 15 sessions in total (5 per week)

Waiting list: no intervention during the first three weeks, afterwards active stimulation: 1 Hz stimulation of 17 mins over left SMA, 15 sessions in total (5 per week)

8.1.3 Packaging, Labelling and Supply (re-supply)

Not applicable.

8.1.4 Storage Conditions

TMS devices are stored in the institution (translational research center at the University Hospital of Psychiatry, Bern) according to internal regulations and the device manual.

8.2 Administration of experimental and control interventions

8.2.1 Experimental Intervention

The application of the TMS device follows the published guidelines^{1,2} and the device manual. Before each session, the resting motor threshold is determined to identify the individual intensity of stimulation. The position for the coil placement is left SMA, which is determined either via neuronavigation using individual brain anatomy or 3 cm anterior of the leg motor area, which is individually determined through single pulse stimulations causing leg movements.

Both experimenter and participants will wear earplugs for auditory safety.

Active experimental protocol:

Lf-rTMS at 1Hz will be used with 1'000 pulses at an intensity of 110% of the resting motor threshold (approximate duration 17 minutes). The protocol is identical to that of our previous study and a study in Parkinson's disease⁷⁷. 15 sessions in total (5 per week)

8.2.2 Control Intervention

Placebo control: 1 Hz stimulation of 17 mins over left SMA without magnetic emission, using the Placebo-coil. 15 sessions in total (5 per week)

Active control: Stimulation parameters for iTBS will follow those of Huang et al.¹⁰⁰, including 600 pulses at 50 Hz (stimulation in 2 sec trains every 10 sec for 190 sec in total). To increase the effect, we will deliver two iTBS series in one session separated by 15 min with a total of 1200 pulses. During the experiment, iTBS pulse intensity is adjusted to 80% of the motor threshold. iTBS stimulation of 21 mins over left SMA, 15 sessions in total (5 per week)

Waiting list: same protocol as active experimental protocol but only between week 3 and 6.

8.3 Dose / Device modifications

In case of intolerable side effects, the study will be discontinued for the participant. No dose or device modifications are planned.

8.4 Compliance with study intervention

Investigators have to document the order of stimulation. This will be checked for consistency with the group allocation. No further strategies are needed. Participants are always under observation during the rTMS sessions and the planned assessments. Non-compliance on the side of the participant would lead to study discontinuation for this person. Use of concomitant medication will be retrieved from the medical files of the patients and transferred to the CRF.

8.5 Data Collection and Follow-up for withdrawn participants

If participants withdraw their consent, they will be contacted immediately to clarify whether there were intolerance issues with the study. See section 9.2.5 for safety follow-up measures. In case of withdrawal the data will be analyzed and stored encrypted as all the data of the other participants. However, we will remove the encryption key for the participants who withdrew consent and therefore it will not be possible to identify the subjects from encrypted data. Patients who withdrew consent will be invited for the 6 month follow-up interview using their preferred way of contact (Email, letter).

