9.2.4.3 Vital signs

No routine measurement of vital signs is planned. If patients report dizziness, clinical routines will include measurement of blood pressure and heart rate.

9.2.5 **Assessments in participants who prematurely stop the study**

Participants who prematurely stop the study will be immediately assessed for adverse events. In case of adverse events reports, a physical examination will be conducted and results will be recorded accordingly. Follow-up examinations will be planned within the next 14 days in case of continuing problem related to adverse events, and these examinations will be continued every 14 days until the health issue is resolved.

9.3 **Procedures at each visit**

9.3.1 **Screening visit**

- Check the inclusion and exclusion criteria, use CRF
- Collect demographic data, use CRF
- Conduct urine pregnancy test in female participants between 18 and 50 years of age
- Assess diagnoses with SCID, document results in CRF
- Assess handedness with EHI¹⁰¹, document result in CRF
- Assess medical history in CRF

See table study events at 9.1

9.3.2 **Visit 2 (baseline, week 0)**

- Assess current psychopathology, use PANSS interview and BNSS, document in CRF
- Assess formal thought disorder, use TALD interview, document in CRF
- Assess Neurological soft signs, use NES, document in CRF
- Assess psychiatric history with CASH interview in patients, document result in CRF
- Assess primary outcome with SRRS scale, document in CRF
- Assess motor behaviour with rating scales, use BFCRS, UPDRS, AIMS, document results in CRF
- Assess functioning, use GAF, SOFAS, and UPSA-brief, document results in CRF
- Hand out self-rating questionnaires SNS and IPAQ, collect and document in CRF
- Conduct coin rotation test, record on video
- Record gross motor activity using actigraphy
- Test cortical excitability using the TMS device according to standard procedure. Record electronic data
- Acquire MRI scans at University Institute of Diagnostic and Interventional Neuroradiology
- Acquire posturography at University Hospital, Dept. of Neurology, record electronic data
- Record current medication regime in CRF
- Schedule 5 rTMS sessions
- Schedule next visit

9.3.3 **Visit 3 and 4 (week 1 and 2)**

- Assess primary outcome with SRRS scale, document in CRF
- Assess side effects with questions in the CRF
- Record current medication regime in CRF
- Schedule 5 rTMS sessions
- Schedule next visit

9.3.4 **Visit 5 (end of intervention, week 3)**

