11.5 Handling of missing data and drop-outs

We will apply the last-observation-carried-forward (LOCF) method in the final analyses. In case a patient withdraws consent before the first rTMS stimulation, we will recruit an additional patient. The number of all patients recruited and randomized will be reported in the publications.

Sensitivity analyses will be performed in order to establish whether premature dropout would influence the results. Therefore, the primary analyses will be repeated with all subjects who completed the interventional trial. Further tests will establish whether drop-outs differ from completers in basic clinical or demographic variables.

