12.2 Data management

Data of all participants will be encrypted and analysis will be performed using encrypted data only. Unblinding of participant-specific data is only possible after consent has been given by the participants and the sponsor. Data of all participants will receive a numerical identification. The key to this encryption code will be stored in a single file at the address below, and it will be accessible only by the sponsor and the principal investigator.

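### Section 8.5 does not say when the identity key of patients who withdraw consent is removed, and patients who only stop rTMS have no planned SRRS ratings

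*Combined protocol and SAP*

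**What the plan says.** Section 8.5 makes three statements about patients who withdraw consent.

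- Data already collected are kept: "In case of withdrawal the data will be analyzed and stored encrypted as all the data of the other participants".
- The link to identity is cut: "we will remove the encryption key for the participants who withdrew consent", so that nobody can be identified from the coded data.
- They are contacted again: "Patients who withdrew consent will be invited for the 6 month follow-up interview using their preferred way of contact".

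Section 12.2 describes the key: "The key to this encryption code will be stored in a single file at the address below", open only to the sponsor and the principal investigator. No section gives the time of removal, the code under which a returning patient is recorded, or whether the 6-month data are linked.

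Section 7.4 names discontinuing the trial and withdrawing consent as separate events. Section 8.3 ends the study for a participant with intolerable side effects, and section 8.4 does so for non-compliance. For people who leave early, section 9.2.5 says "Participants who prematurely stop the study will be immediately assessed for adverse events" and adds examinations every 14 days while a problem continues. It lists no SRRS rating. Section 11.5 says "We will apply the last-observation-carried-forward (LOCF) method in the final analyses" and adds a sensitivity analysis in completers.

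**The concern.** There are two separate gaps.

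The first concerns the key. The week-24 analyses are changes from baseline compared between groups (section 11.4.3, Hypothesis 4b), so each week-24 rating must be joined to that patient's baseline and arm. If the key no longer exists when the patient returns, the planned link is missing. A real rating would go unused and an earlier one would be carried forward in its place.

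The second concerns patients who stop rTMS but still consent. The plan gives them no outcome visit, so their SRRS values after stopping are imputed. For groups 1 to 3 that includes the week-3 primary endpoint. Patients leaving for intolerance or deterioration are unlikely to be a random subset. If stopping differs between arms, carried-forward values can bias the between-arm comparison.

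**Working it through.** **The plan's own figure.** Section 11.2 gives 88 patients from f = 0.23, correlation 0.5, alpha 0.05, power 0.95, k = 4 groups and m = 2 times. For the group-by-time interaction, lambda = f² × N × m / (1 − rho) = 0.0529 × 88 × 2 / 0.5 = 18.62, with (k − 1)(m − 1) = 3 and (N − k)(m − 1) = 84 degrees of freedom. Power is 0.957, and 88 is the smallest multiple of four that reaches 0.95. The figure reproduces. It concerns baseline to week 3, before the 6-month visit, so the key question does not touch it.

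**Timing of key removal.** The outcome depends on a date that the plan does not give.

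| Key removed | 6-month data linked through the key? | Non-identifiability |
|---|---|---|
| At withdrawal | No | From withdrawal on |
| After the 6-month contact | Yes | Only from then on |

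**Other routes to a link.** Section 12.1.1 puts the year of birth into the participant code, and sections 6.2.1 and 7.3 allocate arms from a list in enrolment order held by the principal investigator. Ages 18 to 60 give 43 birth-year values. Assuming uniform birth years, a returning patient's year is unique among w withdrawn patients with probability (42/43)^(w−1):

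- w = 5: 0.91
- w = 10: 0.81
- w = 15: 0.72

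Re-linking would often be possible without the key, but using it would undo the non-identifiability that 8.5 promises.

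**Number of patients.** The documents give no withdrawal rate. Assume that 10–20% leave early, half of these withdraw consent, and 25–50% of those attend at 6 months.

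- Low: 88 × 0.10 × 0.5 × 0.25 = 1.1
- High: 88 × 0.20 × 0.5 × 0.50 = 4.4

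This is about 1 to 4 patients. If 4 dropped out of a week-24 comparison entirely, N = 84 and power on the planning inputs would be 0.947 instead of 0.957. This borrows the week-3 effect size, because the plan states none for week 24. The loss of precision is small.

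**Patients who stop rTMS.** Read together, the sections give this:

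- Section 11.4.1 keeps everyone with at least one rTMS session in the analysis.
- Sections 8.3 and 8.4 end the study for those who stop, and 9.2.5 lists only adverse-event checks.
- The 6-month invitation in 8.5 is worded only for withdrawn consent.
- Section 11.5 fills the gap with LOCF.

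A patient in groups 1 to 3 who stops after the week-1 rating has that rating carried to week 3. One who stops before it has a recorded change of zero. If the carried value differs from the true week-3 value by δ, the arm mean of 22 moves by δ/22, or 4.5% of δ, per such patient. Equal shifts cancel between arms; unequal ones do not. The waiting group starts rTMS at week 3, so stopping rTMS cannot affect its week-3 rating. This route to the primary endpoint therefore exists only in the other three arms (3 × 22 = 66 patients).

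The completers-only analysis removes these same patients. It shows whether results change without them, not what their week-3 scores were.

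**The case against.** On the key, the strongest reply is that nothing in 8.5 is impossible. If the key is removed after the 6-month contact, every sentence in the section can be followed. That stands. A reader might infer that the rules contradict each other, or that the follow-up data can never be joined. The documents do not support either, because the removal time is missing and other partial routes exist.

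Patients are also only invited. Someone who does not attend has no week-24 value whatever happens to the key, so counting every patient who withdraws consent would overstate the loss.

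A reader might infer that safety follow-up loses its link as well. This is not shown: adverse events are assessed at the time of stopping, and section 12.1.2 keeps extra safety examinations on paper in the same folders as the CRF.

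It is tempting to say that 8.5 merges stopping treatment with withdrawing consent. It limits key removal and the invitation to withdrawn consent, and section 7.4 names both events. What stands is narrower: nothing sets out outcome collection for patients who stop rTMS and still consent.

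Finally, the consent form and study information were not available, and holding a key after consent is withdrawn is a privacy decision. Both points stand, which is why any delay needs the patient's agreement.

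**Conclusion.** Both gaps are real and cheap to close.

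The key gap is a missing time point. Its effect is confined to the week-24 secondary comparisons and to patients who withdraw consent and still attend. The range of about 1 to 4 of 88 rests wholly on the assumed rates above. The week-3 primary analysis and N = 88 are untouched by it.

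The second gap reaches further, because it replaces obtainable week-3 SRRS values with carried-forward ones in the three arms stimulated from baseline. Its size cannot be stated: the documents give neither a stopping rate nor the difference between carried and true values. Bias in the comparison requires that stopping, or that difference, varies by arm, and the documents neither show nor exclude this.

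**What to change.** 1. In section 8.5, state that the key is removed once the 6-month contact is completed or declined and any safety follow-up is closed, with the patient's agreement and matching wording in the consent form. Otherwise, state that 6-month data from patients who withdrew consent will not be linked.
2. In sections 8.5 and 9.2.5, separate stopping rTMS from withdrawing consent. Ask patients who only stop rTMS to attend the SRRS visits already scheduled (weeks 3, 6 and 24; for the waiting group, its own scheduled visits). Use the observed values in the intention-to-treat analysis instead of LOCF.

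The rules for when stimulation stops are not part of this change. The cost is a few more ratings at existing visits, later key removal for patients who agree to it, and revised protocol and consent wording. If the change counts as a substantial amendment, section 2.10 requires ethics committee approval first.

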8.6 Trial specific preventive measures

No specific preventive measures are needed.

8.7 Concomitant Interventions (treatments)

Current medication will be recorded in the CRF at study entry and throughout the 3 week intervention period. Patients are expected to comply with the treatment they are receiving from their treating physicians.

Because this is an add-on treatment, we expect relevant changes from concomitant interventions. Therefore, we apply placebo, waiting-list, and an active control group.

8.8 Study Drug / Medical Device Accountability

Not applicable.

8.9 Return or Destruction of Study Drug / Medical Device

The TMS devices are already in use in the clinic. No study specific procedures are intended.

9. STUDY ASSESSMENTS

9.1 Study flow chart(s) / table of study procedures and assessments

Flow charts are distinct for controls and patients, because controls receive no intervention. Furthermore, three patient groups will start interventions immediately (lf-rTMS, iTBS, and Placebo; i.e. groups 1-3), but one group will be waiting for 3 weeks and then enter the intervention phase (waiting group; i.e. group 4).

9.1.1 Patients of treatment groups 1-3

Study Periods	Screening	Treatment, Intervention Period					Follow-up	
		1	2	3	4	5	6	7
Visit								
Time (week)	-1	0	1	2	3	6	24	
Patient Information and Informed Consent	x							
Demographics	x							
CASH and SCID (history)	x							
In- /Exclusion Criteria	x							
Physical Examination	x							
Pregnancy Test	x							
Psychopathology (TALD, NES)		x						
Randomisation		x						
Administer rTMS (5 sessions per week)		x	x	x				
Primary Variable SRRS		x	x	x	x	x	x	
Motor scales UPDRS, BFCRS, AIMS, IPAQ		x			x	x	x	
Psychopathology (PANSS, BNSS, SNS)		x			x	x	x	
Actigraphy and coin rotation		x			x	x	x	
Posturography		x			x			
TMS cortical excitability		x			x	x	x	
Cerebral MRI		x			x			
Functional outcome (SOFAS, GAF, UPSA-brief)		x				x	x	
Concomitant Therapy		x	x	x	x			
Adverse Events		x	x	x	x			

Study events patient groups 1-3

Visit	Information	Instrument used	Expected time
1 (Screening)	Check inclusion / exclusion criteria	CRF	5 min
	Demographic data	CRF	5 min
	Medical history	CRF	10 min
	Handedness	Edinburgh Handedness Inventory ¹⁰¹	5 min
	Pregnancy test	Urine based test	10 min
	Diagnoses ascertainment	SCID interview	60 min
2 (baseline)	Psychopathology	Positive And Negative Syndrome Scale (PANSS) ⁹³ interview, CASH ¹⁰² interview, Brief Negative Symptom Scale (BNSS) ⁹⁴ ,	90 min

		Thought and Language Disorder (TALD) ¹⁰³ , Neurological Evaluation Scale (NES) ¹⁰⁴	
	Primary outcome	SRRS ⁹²	5 min
	Motor scales	Unified Parkinson's Disease Rating Scale (UPDRS) ¹⁰⁵ , Bush Francis Catatonia Rating Scale (BFCRS) ¹⁰⁶ , Abnormal Involuntary Movement Scale (AIMS) ¹⁰⁷	15 min
	Self Report	Self-Evaluation of negative symptoms (SNS) ⁹⁶ , International Physical Activity Questionnaire (IPAQ) ⁹⁵	10 min
	Motor tests	Actigraphy and coin rotation	5 min
	Posturography	Kistler platform at Dept. of Neurology	30 min
	Cortical excitability	TMS paradigm with paired pulse stimulation	30 min
	Neuroimaging	MRI scan including structural T1, Arterial spin labelling, BOLD resting state and task fMRI	60 min
	Functional outcome	Global Assessment of Functioning GAF, Social and Occupational Functioning Scale SOFAS, UPSA-brief assessment of functional capacity	15 min
	rTMS	5 rTMS daily sessions à 20 min	100 min
3 (week 1)	Primary outcome	SRRS	5 min
	rTMS	5 rTMS daily sessions à 20 min	100 min
	Check side effects	CRF	5 min
	Concomitant therapy	CRF	5 min
4 (week 2)	Primary outcome	SRRS	5 min
	rTMS	5 rTMS daily sessions à 20 min	100 min
	Check side effects	CRF	5 min
	Concomitant therapy	CRF	5 min
5 (week 3)	Psychopathology	Positive And Negative Syndrome Scale (PANSS) ⁹³ interview, Brief Negative Symptom Scale (BNSS) ⁹⁴	30 min
	Primary outcome	SRRS ⁹²	5 min
	Motor scales	Unified Parkinson's Disease Rating Scale (UPDRS) ¹⁰⁵ , Bush Francis Catatonia Rating Scale (BFCRS) ¹⁰⁶ , Abnormal Involuntary Movement Scale (AIMS) ¹⁰⁷	15 min
	Self Report	Self-Evaluation of negative symptoms (SNS) ⁹⁶ , International Physical Activity Questionnaire (IPAQ) ⁹⁵	10 min
	Motor tests	Actigraphy and coin rotation	5 min

	Posturography	Kistler platform at Dept. of Neurology	30 min
	Cortical excitability	TMS paradigm with paired pulse stimulation	30 min
	Neuroimaging	MRI scan including structural T1, Arterial spin labelling, BOLD resting state and task fMRI	60 min
	Functional outcome	Global Assessment of Functioning GAF, Social and Occupational Functioning Scale SOFAS, UPSA-brief assessment of functional capacity	15 min
	Check side effects	CRF	5 min
	Concomitant therapy	CRF	5 min
6 (week 6)	Psychopathology	Positive And Negative Syndrome Scale (PANSS) ⁹³ interview, Brief Negative Symptom Scale (BNSS) ⁹⁴	30 min
	Primary outcome	SRRS ⁹²	5 min
	Motor scales	Unified Parkinson's Disease Rating Scale (UPDRS) ¹⁰⁵ , Bush Francis Catatonia Rating Scale (BFCRS) ¹⁰⁶ , Abnormal Involuntary Movement Scale (AIMS) ¹⁰⁷	15 min
	Self Report	Self-Evaluation of negative symptoms (SNS) ⁹⁶ , International Physical Activity Questionnaire (IPAQ) ⁹⁵	10 min
	Motor tests	Actigraphy and coin rotation	5 min
	Cortical excitability	TMS paradigm with paired pulse stimulation	30 min
	Functional outcome	Global Assessment of Functioning GAF, Social and Occupational Functioning Scale SOFAS, UPSA-brief assessment of functional capacity	15 min
7 (week 24)	Psychopathology	Positive And Negative Syndrome Scale (PANSS) ⁹³ interview, Brief Negative Symptom Scale (BNSS) ⁹⁴	30 min
	Primary outcome	SRRS ⁹²	5 min
	Motor scales	Unified Parkinson's Disease Rating Scale (UPDRS) ¹⁰⁵ , Bush Francis Catatonia Rating Scale (BFCRS) ¹⁰⁶ , Abnormal Involuntary Movement Scale (AIMS) ¹⁰⁷	15 min
	Self Report	Self-Evaluation of negative symptoms (SNS) ⁹⁶ , International Physical Activity Questionnaire (IPAQ) ⁹⁵	10 min
	Motor tests	Actigraphy and coin rotation	5 min
	Cortical excitability	TMS paradigm with paired pulse stimulation	30 min
	Functional outcome	Global Assessment of Functioning GAF, Social and Occupational Functioning	15 min

		Scale SOFAS, UPSA-brief assessment of functional capacity	
--	--	---	--

9.1.2 Patients of treatment group 4 (waiting group)

Study Periods	Screening	Treatment, Intervention Period					Follow-up	
		1	2	3	4	5	6	7
Visit	1	2	3	4	5	6	7	8
Time (week)	-1	0	3	4	5	6	9	24
Patient Information and Informed Consent	x							
Demographics	x							
CASH and SCID (history)	x							
In- /Exclusion Criteria	x							
Physical Examination	x							
Pregnancy Test	x							
Psychopathology (TALD, NES)		x						
Randomisation		x						
Administer rTMS (5 sessions per week)			x	x	x			
Primary Variable SRRS		x	x	x	x	x	x	x
Motor scales UPDRS, BFCRS, AIMS, IPAQ		x	x			x	x	x
Psychopathology (PANSS, BNSS, SNS)		x	x			x	x	x
Actigraphy and coin rotation		x	x			x	x	x
Posturography		x	x			x		
TMS cortical excitability		x	x			x	x	x
Cerebral MRI		x	x			x		
Functional outcome (SOFAS, GAF, UPSA-brief)		x	x				x	x
Concomitant Therapy		x	x	x	x	x		
Adverse Events			x	x	x	x		

Study events for patients of the waiting group

Visit	Information	Instrument used	Expected time
1 (Screening)	Check inclusion / exclusion criteria	CRF	5 min
	Demographic data	CRF	5 min
	Medical history	CRF	10 min
	Handedness	Edinburgh Handedness Inventory ¹⁰¹	5 min
	Pregnancy test	Urine based test	10 min
	Diagnoses ascertainment	SCID interview	60 min
2 (baseline)	Psychopathology	Positive And Negative Syndrome Scale (PANSS) ⁹³ interview, CASH ¹⁰² interview, Brief Negative Symptom Scale (BNSS) ⁹⁴ , Thought and Language Disorder (TALD) ¹⁰³ , Neurological Evaluation Scale (NES) ¹⁰⁴	90 min

	Primary outcome	SRRS ⁹²	5 min
	Motor scales	Unified Parkinson's Disease Rating Scale (UPDRS) ¹⁰⁵ , Bush Francis Catatonia Rating Scale (BFCRS) ¹⁰⁶ , Abnormal Involuntary Movement Scale (AIMS) ¹⁰⁷	15 min
	Self Report	Self-Evaluation of negative symptoms (SNS) ⁹⁶ , International Physical Activity Questionnaire (IPAQ) ⁹⁵	10 min
	Motor tests	Actigraphy and coin rotation	5 min
	Posturography	Kistler platform at Dept. of Neurology	30 min
	Cortical excitability	TMS paradigm with paired pulse stimulation	30 min
	Neuroimaging	MRI scan including structural T1, Arterial spin labelling, BOLD resting state and task fMRI	60 min
	Functional outcome	Global Assessment of Functioning GAF, Social and Occupational Functioning Scale SOFAS, UPSA-brief assessment of functional capacity	15 min
3 (week 3)	Psychopathology	Positive And Negative Syndrome Scale (PANSS) ⁹³ interview, CASH ¹⁰² interview present part only, Brief Negative Symptom Scale (BNSS) ⁹⁴ , Thought and Language Disorder (TALD) ¹⁰³ , Neurological Evaluation Scale (NES) ¹⁰⁴	90 min
	Primary outcome	SRRS ⁹²	5 min
	Motor scales	Unified Parkinson's Disease Rating Scale (UPDRS) ¹⁰⁵ , Bush Francis Catatonia Rating Scale (BFCRS) ¹⁰⁶ , Abnormal Involuntary Movement Scale (AIMS) ¹⁰⁷	15 min
	Self Report	Self-Evaluation of negative symptoms (SNS) ⁹⁶ , International Physical Activity Questionnaire (IPAQ) ⁹⁵	10 min
	Motor tests	Actigraphy and coin rotation	5 min
	Posturography	Kistler platform at Dept. of Neurology	30 min
	Cortical excitability	TMS paradigm with paired pulse stimulation	30 min
	Neuroimaging	MRI scan including structural T1, Arterial spin labelling, BOLD resting state and task fMRI	60 min
	Functional outcome	Global Assessment of Functioning GAF, Social and Occupational Functioning Scale SOFAS, UPSA-brief assessment of functional capacity	15 min
	rTMS	5 rTMS daily sessions à 20 min	100 min
4 (week 4)	Primary outcome	SRRS	5 min

	rTMS	5 rTMS daily sessions à 20 min	100 min
	Check side effects	CRF	5 min
	Concomitant therapy	CRF	5 min
5 (week 5)	Primary outcome	SRRS	5 min
	rTMS	5 rTMS daily sessions à 20 min	100 min
	Check side effects	CRF	5 min
	Concomitant therapy	CRF	5 min
6 (week 6)	Psychopathology	Positive And Negative Syndrome Scale (PANSS) ⁹³ interview, Brief Negative Symptom Scale (BNSS) ⁹⁴	30 min
	Primary outcome	SRRS ⁹²	5 min
	Motor scales	Unified Parkinson's Disease Rating Scale (UPDRS) ¹⁰⁵ , Bush Francis Catatonia Rating Scale (BFCRS) ¹⁰⁶ , Abnormal Involuntary Movement Scale (AIMS) ¹⁰⁷	15 min
	Self Report	Self-Evaluation of negative symptoms (SNS) ⁹⁶ , International Physical Activity Questionnaire (IPAQ) ⁹⁵	10 min
	Motor tests	Actigraphy and coin rotation	5 min
	Posturography	Kistler platform at Dept. of Neurology	30 min
	Cortical excitability	TMS paradigm with paired pulse stimulation	30 min
	Neuroimaging	MRI scan including structural T1, Arterial spin labelling, BOLD resting state and task fMRI	60 min
	Functional outcome	Global Assessment of Functioning GAF, Social and Occupational Functioning Scale SOFAS, UPSA-brief assessment of functional capacity	15 min
	Check side effects	CRF	5 min
Concomitant therapy	CRF	5 min	
7 (week 9)	Psychopathology	Positive And Negative Syndrome Scale (PANSS) ⁹³ interview, Brief Negative Symptom Scale (BNSS) ⁹⁴	30 min
	Primary outcome	SRRS ⁹²	5 min
	Motor scales	Unified Parkinson's Disease Rating Scale (UPDRS) ¹⁰⁵ , Bush Francis Catatonia Rating Scale (BFCRS) ¹⁰⁶ , Abnormal Involuntary Movement Scale (AIMS) ¹⁰⁷	15 min
	Self Report	Self-Evaluation of negative symptoms (SNS) ⁹⁶ , International Physical Activity Questionnaire (IPAQ) ⁹⁵	10 min

	Motor tests	Actigraphy and coin rotation	5 min
	Cortical excitability	TMS paradigm with paired pulse stimulation	30 min
	Functional outcome	Global Assessment of Functioning GAF, Social and Occupational Functioning Scale SOFAS, UPSA-brief assessment of functional capacity	15 min
8 (week 24)	Psychopathology	Positive And Negative Syndrome Scale (PANSS) ⁹³ interview, Brief Negative Symptom Scale (BNSS) ⁹⁴	30 min
	Primary outcome	SRRS ⁹²	5 min
	Motor scales	Unified Parkinson's Disease Rating Scale (UPDRS) ¹⁰⁵ , Bush Francis Catatonia Rating Scale (BFCRS) ¹⁰⁶ , Abnormal Involuntary Movement Scale (AIMS) ¹⁰⁷	15 min
	Self Report	Self-Evaluation of negative symptoms (SNS) ⁹⁶ , International Physical Activity Questionnaire (IPAQ) ⁹⁵	10 min
	Motor tests	Actigraphy and coin rotation	5 min
	Cortical excitability	TMS paradigm with paired pulse stimulation	30 min
	Functional outcome	Global Assessment of Functioning GAF, Social and Occupational Functioning Scale SOFAS, UPSA-brief assessment of functional capacity	15 min

